The number of samples required to understand the impact of environmental or physiological confounds on surface temperature is dependent on the variability in the core-to-surface temperature physiologic offset. The variability in core body temperature has been found to be close to 1F but note the research design proposed here is not dependent on normal person-to-person variability in core temperature because the temperatures obtained are all referenced to each individual's core temperature. To estimate the likely physiologic variability in the population, we can extrapolate based on surface temperature data taken by the primary thermographic system obtained over the past six months because this should be approximately the vector sum of variability in core temperature, measurement accuracy, and the physiologic variability. This data must be interpreted with caution, because these have been obtained with less control over environmental conditions and furthermore we do not know the core body temperature variability in the preliminary data population, but it can provide a reasonable error bound. This data shows a standard deviation of 1.11F (note, this value is obtained without *any* bias-to-normal algorithm, which appears to be a novel feature in this research), which would suggest the physiologic variability component is at most 0.48F, or half a degree. Therefore, in order to determine the sensitivity and specificity at detecting elevated temperatures of 1.8F (100.4F threshold) to within 20% (meaning, can we significantly distinguish 100.40 from 100.04F with the aforementioned standard deviation in a one-sided paired t-test), we require 28 participants. To account for possible data collection failures, we intend to recruit as many as 45 participants.

Data Collection

- Demographic and clinical data: minimal demographic and clinical data will be collected by interview with the participant at the time of the imaging studies including age, gender, any disease- or autonomic-modulating treatment, height, weight and any antipyretic medications in past 12 hours in order to allow adjustment for confounding factors. We do not intend to collect data on menstrual cycle due to the additional potential privacy concerns this will place on participants worried about this data which is significantly more sensitive than other data being collected.

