Each participant is directed to go to one of two rooms (labelled D or E, used for *heating* or *cooling*), enter as directed by a study personnel, scan their NFC sticker to enable their **nfc-equilibration-scan**, and subsequently sit in front of the primary thermographic system for 10 minutes. The subject may freely close their eyes and move around as long as their eye locations are visible by the camera system, which is aided by instructions provided by the operator to "ensure that at nearly all times you can see the lens of the thermal camera", with a picture as below posted nearby. At the conclusion of the serial measurement, study personnel will obtain an oral thermometry measurement. This process is repeated in the second room.

You may move around and close your eyes freely but please make sure both eyes are in view of the thermal image lens (see arrow) at all times.

Periodically check that you can see the entire ring (red circle) with both eyes.

Timing of Study Procedures

By appointing five rooms and interleaving equilibration times with scan times, it is possible to complete all measurements above on 9 subjects in 94 minutes, plus up to a 15-minute break in the middle of procedures. Briefly, every two minutes, one of the nine subjects is given a letter, whereupon they proceed to said lettered room to wait for 10 minutes to equilibrate for the blinded portion. The random letter drawing process is balanced so at most times, there are no more than 2 subjects in the room at a time. After the ten minutes is complete for a participant, study personnel will direct the participant to the scanning area. A third of the time, a new participant will be entering about the same time as a participant is leaving the room. The participant obtaining a scan will walk to the scan area, receive their primary scan, then any secondary scans, requiring a total of two minutes. Then the participant will receive a monitor-mode oral temperature, requiring up to two minutes. There will be approximately 4 minutes between this time and when the participant should go to the next lettered room for a ten minute equilibration time. This process repeats until all three rooms are complete, at which point the subjects are given an opportunity to have a break for up to 15 minutes. Note, we will interview subjects at the start of their break time and if they wish to begin sooner than 15 minutes and if the sequencing permits, the subject may proceed with less than a 15 minute break.

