Once the break time is concluded for each subject, the process switches to the equilibration time measurement. Participants will wait an extra six minutes before proceeding to one of the rooms, in alternating order, so after ten minutes, the participant simply switches to the other equilibration room. A spreadsheet demonstrating the sequencing is included in the protocol materials, showing the time (10:00AM is selected as the start time for demonstrative purposes) in two-minute increments for 100 minutes, the participant (out of nine) who is currently switching rooms, the room they are being sent to (lettered A-E), which person is receiving the

thermographic scan, which person is receiving an oral measurement and the number of people at any given time in each room.

C. Safety

The risk to the participants participating in this study is low. Thermal imaging is a non-invasive, completely passive procedure. We do not expect any discomfort associated with thermal imaging. Oral thermometry is considered to have no risk, but it is possible participants could experience discomfort with oral thermometry. If participants indicate severe discomfort, the operator will immediately discontinue the procedure. The majority of the population has received a clinical oral thermometry procedure and participants are only eligible if they have received a clinical oral thermometry procedure in the past.

D. Analyses

It is foreseen that the two types of data will be analyzed separately and in two ways each. The equilibration data will be analyzed to determine the physiologic time constant in each dataset and grouped by direction of equilibration (heating, cooling). The groups of time constants will be assessed for significant differences between heating and cooling by two-sample t-test and a 95% confidence threshold. The average and standard deviation time constant (and if these are significantly different, this will be performed separately for heating and cooling) will be recorded and reported in an open-access publication with the rest of the results. The endpoint of each equilibration dataset will also be used to determine a linear physiologic offset (note, the existing parametric physiologic offset was previously determined in a 32-subject sample in June 2020 but for the purposes of this study, we intend to re-evaluate this equation) and the resulting equation and coefficients published along with the equilibration results.

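### Heating and cooling time constants are reported separately only if an unpaired test is significant, so a non-significant result becomes grounds to pool, in a comparison the study was not sized for

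*Combined protocol and SAP*

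**What the plan says.** Section D (Analyses) fits a time constant to each equilibration dataset and groups the results by direction. The groups are then "assessed for significant differences between heating and cooling by two-sample t-test and a 95% confidence threshold". The mean and SD go into an open-access publication, with the parenthesis "if these are significantly different, this will be performed separately for heating and cooling". The plain reading is that, without significance, a single mean and SD cover both directions.

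Both directions are measured in the same people. Under Detailed Procedure - Equilibration Study, each participant sits in one of Rooms D and E for ten minutes, and then: "This process is repeated in the second room". Timing of Study Procedures confirms that "the participant simply switches to the other equilibration room".

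The sample size is under Population Size: "we require 28 participants", and to allow for data collection failures "we intend to recruit as many as 45 participants". The question behind the 28 is "can we significantly distinguish 100.40 from 100.04F" in a one-sided paired t-test. That concerns temperature, not time constants.

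**The concern.** The rule lets a significance test decide which estimate is published. A non-significant result may mean that the directions are alike, or that the test was too weak to separate them, and the plan treats the two cases the same way. It gives no equivalence margin, expected difference, SD or power for time constants. Section D does warn that the small sample may hide correlations between time constants and demographic data, but puts no such caution on heating against cooling.

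The test also does not fit the design. Each participant contributes one constant per direction, so the data are paired, while a two-sample t-test treats them as independent groups. If people who warm slowly also cool slowly, the test overstates the standard error of the difference and leans further towards pooling.

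At stake is a named result of the equilibration phase. If only a pooled mean and SD are printed, a reader cannot recover the two directional values.

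**Working it through.** **1. The plan's own figure.** Inputs from Population Size: difference 100.40 − 100.04 = 0.36F, one-sided paired t-test. Alpha, power and the SD meant are not explicit; alpha 0.05 is assumed. Two readings come to about 28:

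- SD 1.11F, smallest n at which an observed 0.36F is just significant: at n = 28, 1.703 × 1.11/√28 = 0.357, below 0.36; at n = 27, 1.706 × 1.11/√27 = 0.364, above it. So n = 28, with about 51% power.
- SD 0.48F with 99% power, normal approximation: (1.645 + 2.326)² × 0.48²/0.36² ≈ 28.0 (30 by exact t).

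Either way, 28 was derived for a temperature difference and does not carry over to time constants.

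**2. Chance of pooling under the stated test.** Let d be the true heating-cooling difference divided by the SD of the time constant, taken as equal in both directions. Assumptions: two-sided 5% ("by two-sample t-test and a 95% confidence threshold" does not state sidedness), n constants per direction, independence. The noncentrality is d√(n/2) with 2n − 2 degrees of freedom; the chance of pooling is 1 − power. Example, n = 28 and d = 0.5: noncentrality 0.5 × √14 = 1.871, critical value 2.005 on 54 df, power 45%, pooled 55%.

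| True difference d | Pooled, n = 28 | Pooled, n = 45 |
|---|---|---|
| 0.3 SD | 80% | 71% |
| 0.5 SD | 55% | 35% |
| 0.8 SD | 16% | 4% |
| 1.0 SD | 4% | 0.3% |

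The difference detectable with 80% power is 0.76 SD at n = 28 and 0.60 SD at n = 45.

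**3. Effect of ignoring the pairing.** Assume a within-person correlation of 0.5 (not in the documents) and n = 28. The unpaired test needs an observed difference of about 2.005 × √(2/28) = 0.536 SD. The true standard error is √(2 × (1 − 0.5)/28) = 0.189 SD, against the √(2/28) = 0.267 SD that the test uses. A paired test has noncentrality d√n/√(2(1 − 0.5)) = d√28 on 27 df.

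| n = 28, correlation 0.5 | Unpaired test (simulated) | Paired test |
|---|---|---|
| Type I error | about 0.7% | 5% |
| Pooled at 0.3 SD | 88% | 67% |
| Pooled at 0.5 SD | 57% | 28% |

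Pairing lowers the risk, but a significance condition applied to a paired test would still pool real differences.

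**4. Cost of pooling.** With equal numbers per direction, the pooled mean lies midway between the two means, so each direction is off by d/2: 0.25 SD at d = 0.5. Simulated root mean squared error for one direction, n = 28, independence:

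| d | Plan's rule | Always separate |
|---|---|---|
| 0.2 SD | 0.18 | 0.19 |
| 0.5 SD | 0.25 | 0.19 |
| 0.8 SD | 0.23 | 0.19 |

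The pooled SD is inflated by √(1 + d²/4), about 3% at d = 0.5, which is negligible.

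**5. Where the time constant is used.** The stay in Rooms A to C is fixed at ten minutes (Detailed Procedure - Blinded Temperature Study). Fever labels come from the air-temperature difference between room and scanner (section D), and the conversion formulas have the fixed coefficients 0.191 and 0.236 (Controlled Temperature Rooms). The physiologic offset is estimated from the dataset endpoints. None of these steps takes the time constant as an input.

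**The case against.** The strongest reply is that a common constant is a sensible default. The Physiologic Model appendix treats heat loss as linear in the skin-to-air difference, and a simple linear first-order model would give the same time constant in both directions. For small differences the rule also loses nothing in accuracy, as the 0.2 SD row shows. The data are grouped by direction anyway, and the plan does not say that directional values will be withheld. Part of this stands: the documents do not show that the two constants differ. But the appendix concerns static equilibrium and concedes that air conditions can change convective loss by a factor of two or more, so it does not establish equality. Nor does the plan promise directional values when the test is not significant.

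Three stronger readings are tempting and are not supported. A reader might infer that a real difference will often be averaged away. That depends on its size relative to an SD the documents do not give, and above about 0.76 SD it is missed less than 20% of the time even at n = 28. A reader might infer that the published constant will simply be wrong for both directions. The error is half the difference, arises only when a real difference is pooled, and may be small. A reader might infer that a pooled constant distorts the heated-room stay, the loss of heat before scanning, or the sensitivity and specificity results. Step 5 of the working finds no such use of the constant.

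**Conclusion.** The point holds as a reporting flaw of minor severity. Non-significance is used as grounds to pool, nothing sizes the study for this comparison, and the chosen test disregards the within-person design. At n = 28, pooling is more likely than not for true differences up to about 0.5 SD and unlikely from 0.8 SD upward; at the recruitment ceiling of 45 the risk at 0.5 SD falls to 35%. These figures assume a two-sided 5% test, equal SDs, independence, and a usable constant in each direction from every participant. The figures for the unpaired test on paired data also assume a correlation of 0.5. The existence of the rule is certain. How often it would mislead cannot be settled from the documents. The consequence is confined to the published summary of time constants.

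**What to change.** In section D, delete the condition that makes reporting by direction depend on significance. Replace the two-sample t-test with a paired analysis. Suggested wording: *The mean and SD of the time constant will be reported for heating and for cooling in all cases, together with the mean within-person difference (heating minus cooling) and its 95% confidence interval from a paired analysis. A pooled value may be given in addition.*

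This is a change of wording only, with no extra participants, measurements or procedures. If the directions prove alike, the confidence interval will show how closely, and the pooled value is still available. The paired analysis also gains precision if the constants are positively correlated: at n = 28 and an assumed correlation of 0.5, the difference detectable with 80% power falls from 0.76 SD (two-sample test, independence assumed) to 0.55 SD.

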In a second analysis, the equilibration time constants will be evaluated for possible linear correlations with the demographic data, although it is possible the small sample size and variability will preclude the detection of any significant correlations. In case there are nonlinear relations, scatter plots will be examined to determine if a low-order polynomial or other reasonable fit could explain a relation, while keeping in mind the fact each additional test is a multiple comparison, thus increasing the required p-value multiplicatively. Scatter-plots, trends and r-values will be reported, and this data may be collated with future collections of independent datasets.

The controlled face temperature data will be analyzed for sensitivity and specificity of each non-contact system used, first in a blinded analysis and then in an open-label analysis. First, the blinded face temperature data will be used to assign each recorded datapoint into normal, mild and moderate and severe fever groups, corresponding to below 38C (100.4F), 38-39C (100.4-102.2F), 39-40C (102.2-104F) and above 40C (104F). Note, the heated rooms' air temperatures were selected to produce simulated core temperatures that straddle the mild and moderate thresholds (hence, a well-performing system should place 50% of the measurements above the threshold and 50% below while a system relying on a bias-to-normal method might place only 10% above the selected threshold), therefore the severe fevers group

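### The only multiplicity statement, for the exploratory time-constant correlations, is worded in the wrong direction: it raises the significance threshold with each added test

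*Combined protocol and SAP*

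**What the plan says.** Section D (Analyses) plans a second analysis of the equilibration data in which "the equilibration time constants will be evaluated for possible linear correlations with the demographic data". It concedes that the study may be too small, and the data too variable, for any correlation to reach significance. In case a relation is not linear, "scatter plots will be examined to determine if a low-order polynomial or other reasonable fit could explain a relation". The multiplicity statement closes that same sentence: "each additional test is a multiple comparison, thus increasing the required p-value multiplicatively". The promised output is plots, trends and correlation coefficients, possibly combined with later datasets.

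The document names no correction method, number of tests or adjusted alpha. The only significance level stated in the section belongs to a different comparison, heating against cooling time constants, which uses a "two-sample t-test and a 95% confidence threshold".

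The candidate variables come from section B, Data Collection, which lists the demographic and clinical items together: "including age, gender, any disease- or autonomic-modulating treatment, height, weight and any antipyretic medications in past 12 hours". On numbers, section B, Population Size, says "we require 28 participants" and, to allow for data-collection failures, "we intend to recruit as many as 45 participants".

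**The concern.** A p-value that is required for significance is a threshold. A valid adjustment for several tests lowers that threshold, or equivalently raises each observed p-value before comparing it with the unadjusted threshold. The sentence joins the verb that suits the observed p-value to the noun for the threshold. Taken at its word, it allows a result to be called significant at a larger p-value the more relations are examined.

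The direction matters because the sentence covers a search that is open by design: several variables, and curve shapes picked after the data have been seen, in a sample of 28 to 45. This is where chance findings are most likely and where the adjustment is needed. An analyst who followed the text would do worse than one who made no adjustment. A spurious relation between time constant and a demographic variable could then be published and carried into later pooled data.

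**Working it through.** The plan gives no numerical threshold for these tests, so there is no stated figure to reproduce. The check has two parts.

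**Direction.** Let α be the single-test threshold and m the number of tests.
- Standard rule: call a result significant if p < α/m, which is the same as m × p < α. The threshold falls as m rises.
- The plan's sentence, read literally: the threshold is multiplied up, to α × m (capped at 1). The threshold rises as m rises.

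The two coincide only at m = 1. For any m above 1 the literal rule is looser than no adjustment, whatever α is and whether or not the tests are independent.

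**Illustrative size.** Inputs:
- α = 0.05. This is an assumption; the plan states a 95% level only for the heating-versus-cooling test.
- m = 4 if only age, gender, height and weight count as demographic; m = 6 if the treatment and antipyretic items are added. Both are assumptions, with one linear test per variable.
- m = 12 if the six variables are tested separately for heating and cooling. This is a further assumption: the plan separates the summary statistics only if the two directions differ significantly, and does not say that the correlations would be split.
- Tests are taken as independent. Height, weight and gender are unlikely to be so.

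The chance of at least one false positive among m true nulls at per-test threshold a is 1 − (1 − a)^m.

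| m | Literal threshold 0.05 × m | Chance, literal | Chance, unadjusted 0.05 | Divided threshold 0.05/m | Chance, divided |
|---|---|---|---|---|---|
| 4 | 0.20 | 1 − 0.80^4 = 0.59 | 1 − 0.95^4 = 0.185 | 0.0125 | 0.049 |
| 6 | 0.30 | 1 − 0.70^6 = 0.88 | 1 − 0.95^6 = 0.265 | 0.0083 | 0.049 |
| 12 | 0.60 | 1 − 0.40^12 ≈ 1.00 | 1 − 0.95^12 = 0.460 | 0.0042 | 0.049 |

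The same contrast can be put in terms of the correlation needed for significance. With t the two-sided critical value on n − 2 degrees of freedom, the critical |r| is t/√(t² + n − 2). For m = 6:

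| n | Literal (0.30) | Unadjusted (0.05) | Divided (0.0083) |
|---|---|---|---|
| 28 | 0.203 | 0.374 | 0.489 |
| 45 | 0.158 | 0.294 | 0.389 |

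So with 28 participants a correlation of about 0.2 would pass the rule as written, while a corrected rule would ask for about 0.49.

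**The case against.** The strongest reply is that nobody would apply the sentence literally. It is introduced as something to keep in mind when adding tests, it follows an admission that real relations may go undetected, and its reference to multiplication fits the ordinary practice of multiplying observed p-values by the number of tests. That stands: the authors almost certainly meant to tighten. A literal threshold of 0.60 is itself a sign that the literal reading was not intended.

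It is also fair that the sentence is barely a decision rule. It has no alpha and no count of tests, the results are to be reported descriptively, and no step classifies a variable as a confound by its p-value. That limits the consequence. It does not make the sentence right, because the plan does speak of significant correlations and offers no second statement from which the intended rule could be recovered.

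Two stronger readings are tempting, and the documents support neither.
- A reader might infer that nearly every demographic variable would be declared a confound. At m = 6 each null variable has a 30% chance of passing, so 6 × 0.30 = 1.8 false positives are expected. The 0.88 is the chance of at least one.
- A reader might infer that the rule governs the study's secondary goal, the effect of confounds on thermographic measurement. The analysis labelled for that purpose uses each person's physiologic correction parameters from the controlled face temperature data. It borrows the reporting format of the equilibration analysis but does not repeat the multiplicity statement.

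**Conclusion.** The point holds as a minor one. The plan's only multiplicity statement is in the wrong direction as written and is not corrected elsewhere. The direction of the error needs no assumption about alpha, the number of tests or independence. Its size does: the range from 0.59 (m = 4) to 0.88 (m = 6) for a false positive under the literal rule assumes alpha 0.05 and independent tests, and the plan fixes neither alpha nor m for these correlations. The figures show what following the text would do; they do not predict what the investigators will do.

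The scope is the exploratory correlations of equilibration time constants with demographic data and any nonlinear fits added to them. The sensitivity and specificity analyses, the heating-versus-cooling comparison and the sample size do not depend on the sentence.

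**What to change.** Reword the clause along these lines: each additional test is a multiple comparison, so the p-value required for significance is divided by the number of tests examined (equivalently, each observed p-value is multiplied by that number). Add that the number counts every linear and nonlinear fit tried. Because curve shapes are chosen after the plots are seen, the report should list the fits attempted so that the count can be verified. Stating the alpha that is to be divided would make the rule complete, though correcting the direction does not depend on it.

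The cost is one sentence in section D. No data collection, sample size or other analysis changes.
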